#### 6.2.3 ADDITIONAL ANALYSES

In the event of controlling covariates, logistic regression will be used to compare the proportion of subjects achieving an endpoint in each group (PT101 or placebo). Covariates that may be included in the model are oral corticosteroid use, prior advanced therapy use, and baseline measures of mMCS, MES, SF, and RB scores.

#### 6.2.4 MISSING DATA HANDLING

##### 6.2.4.1 Non-responder Imputation

For the responder analyses described in [Table 5](#), subjects who do not have sufficient measurements to determine the endpoint will be considered as non-responders (i.e., non-responder imputation [NRI]). Specifically, all subjects who discontinue from the study at any time prior to the assessment timepoint or fail to have an adequate efficacy assessment at the timepoint will be considered a non-responder. The NRI may be applied at any time point specified for analysis.

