3.1.4 Early Termination or Unscheduled Visit

Subjects who receive \geq 1 dose of study drug should be encouraged to complete all study visits within the IBT phase. If subjects discontinue study drug and terminate early from the study, they will be asked to return to the study site for an early termination (ET) visit approximately 28 days after the last dose of study drug administration. If a subject has an ET visit, the assessments designated in the schedule of events (SOE) should be conducted. In addition, if at any time up to ^{CCI}
[REDACTED]

^{CCI}
[REDACTED] all procedures that were conducted at that visit will be collected in the electronic case report form (eCRF) as an unscheduled visit.

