5.2.2 Prohibited Concomitant Therapy

Some medications and treatments may have an impact on the safety of the subjects and/or efficacy assessments of this study. Prohibited concomitant medications that may impact efficacy assessments or impact subject safety are presented in [Table 1](#). Subjects who initiate any of these concomitant medications at any time during the IBT phase of the study must be discontinued from study drug and will not be eligible for the OL or CBT phase of the study. Subjects who initiate any of these concomitant medications at any time during the OL or CBT phase of the study must be discontinued from study drug.

Medications or vaccinations specifically prohibited in the exclusion criteria and in [Table 1](#) are not allowed during the ongoing study. If there is a clinical indication for any medications or vaccinations specifically prohibited (i.e., as supportive care or to treat AEs as deemed necessary by the investigator or the subject's physician), discontinuation from study drug may be required. The investigator should discuss any questions regarding this with the Medical Monitor. The final decision on any supportive therapy or vaccination rests with the investigator and/or the subject's primary physician. However, the decision to continue the subject on study drug requires the mutual agreement of the investigator, the Sponsor, and the subject.

Table 1: Prohibited Concomitant Medications that May Impact Efficacy Assessments or Impact Subject Safety

Drug Class	Agents Disallowed	Prohibited Period
TNF α antagonist	Infliximab (t $\frac{1}{2}$: 9.5 days) Adalimumab (t $\frac{1}{2}$: 10-20 days) Golimumab (t $\frac{1}{2}$: 12-14 days) Certolizumab (t $\frac{1}{2}$: 14 days)	5 half-lives prior to Day 1* through the end of treatment
Integrin antagonist	Vedolizumab (t $\frac{1}{2}$: 25 days) Natalizumab (t $\frac{1}{2}$: 11 days)	5 half-lives prior to Day 1* through the end of treatment
Interleukin antagonist	Ustekinumab (t $\frac{1}{2}$: 19 days)	5 half-lives prior to Day 1* through the end of treatment
JAK inhibitor	Baricitinib (t $\frac{1}{2}$: 12 hours) Tofacitinib (t $\frac{1}{2}$: 3 hours) Tofacitinib XR (t $\frac{1}{2}$: 6-8 hours) Upadacitinib (t $\frac{1}{2}$: 8-14 hours)	5 half-lives prior to Day 1* through the end of treatment
S1P1 inhibitor	Fingolimod (t $\frac{1}{2}$: 6-9 days) Ozanimod (t $\frac{1}{2}$: 11 days) Siponimod (t $\frac{1}{2}$: 30 hours)	5 half-lives prior to Day 1* through the end of treatment

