5.2.3.1 Corticosteroid Tapering

A steroid taper should be initiated for responders at Week 12 of the IBT phase for subjects entering the CBT phase. For non-responders at Week 12 of the IBT phase, the steroid taper should be initiated at Week 24 of the OL phase only for subjects who have achieved a clinical response defined by the partial Mayo Score. The dose should be reduced at a rate starting at 2.5 mg per week up to 5 mg per week for prednisone (or equivalent taper if not prednisone) until the subject is no longer on steroids. Budesonide should be tapered by 3 mg every 2–3 weeks until the subject is no longer taking budesonide. For subjects undergoing steroid taper, steroids may be increased or restarted at doses up to and including their screening dose if return of symptoms is apparent. Subjects who are unable to steroid taper will be allowed to continue in the study. Subjects who need to increase their steroid dose beyond the maximum dose for allowed concomitant therapy use or increase their steroid treatment dose over their screening dose must be discontinued from the study.

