#### 6.2.1.1 Statistical Methods for Dichotomous Efficacy Endpoints

The proportion of subjects achieving each of the dichotomous efficacy endpoints defined in [Table 5](#) will be summarized by treatment group using frequency distribution. To compare the proportion of subjects at a timepoint [CCI](#) the Cochran-Mantel-Haenszel (CMH) method will be used, and an exact 95% CI will be estimated. Missing values in the categorical endpoints will be imputed as non-responders. All dichotomous efficacy endpoints will be listed in by-subject listings.

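### The non-responder rule does not cover starting a prohibited UC medication, so the plan permits such a subject to be scored as a Week 12 responder

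*SAP*

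**What the plan says.** SAP Section 6.2.4.1 opens with a general rule: "subjects who do not have sufficient measurements to determine the endpoint will be considered as non-responders". It then makes this specific, naming "all subjects who discontinue from the study at any time prior to the assessment timepoint or fail to have an adequate efficacy assessment" at that timepoint. Section 6.2.1.1 restates the rule more narrowly: "Missing values in the categorical endpoints will be imputed as non-responders". SAP Table 5 defines each binary endpoint by scores alone. Efficacy is analyzed primarily on the ITT set (SAP Sections 4.2.1 and 6).

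Protocol Section 5.2.2 says that subjects who start a Table 1 medication during the initial blinded treatment (IBT) phase "must be discontinued from study drug and will not be eligible for the OL or CBT phase of the study". Table 1 covers TNF, integrin and interleukin antagonists, JAK and S1P1 inhibitors, rectal mesalamine and corticosteroids, antidiarrheals and others. The same section later says, of prohibited medications given for a clinical indication, that "discontinuation from study drug may be required". A footnote to Table 1 lets a subject who took an antidiarrheal by mistake for one or two days stay in, with approval.

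Protocol Section 3.1.4 says that subjects who received at least one dose "should be encouraged to complete all study visits within the IBT phase".

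**The concern.** The event that stops study drug is not an event that triggers non-response. A subject whose UC is not controlled may start, for example, a TNF antagonist at Week 5, come off study drug, attend Week 12, and have a complete Mayo score and endoscopy. Under the SAP that subject is scored on those data, although any improvement may come from the other drug. On placebo this raises the comparator rate and hides a PT101 effect; on PT101 it inflates the rate. The endpoints exposed are the binary ones in SAP Table 5. They are exploratory, but Protocol Section 9.3.4 and SAP Section 13.1 both say that safety and efficacy together inform the choice of dose and regimen for later development.

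**Working it through.** **Step 1: the triggers.** The SAP gives three routes to non-response: too few measurements, leaving the study before the timepoint, and no adequate assessment. A subject who is off study drug, still in the study and fully assessed meets none of them.

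**Step 2: what happens to a Table 1 starter.** Protocol Section 5.2.2 has two consequences: off study drug, and no entry to the later phases. It does not end study participation. Section 3.1.4 sends to an early termination visit those who stop study drug and also leave the study, so it treats these as two events.

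**Step 3: a contrast within the protocol.** Section 5.2.3.1, on steroid tapering, says that subjects who "increase their steroid treatment dose over their screening dose must be discontinued from the study". Leaving the study does trigger the SAP rule. The difference between leaving study drug and leaving the study thus decides how a subject is scored, and Section 5.2.2 uses the former.

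**Step 4: the existing safeguards.** SAP Section 4.2.3 defines two per-protocol sets. PP1 removes subjects on concomitant corticosteroids and does nothing about biologics or JAK inhibitors. PP2 removes subjects with major deviations that could affect efficacy, as judged at a blinded review. If a Table 1 start is judged major, PP2 drops the subject from the denominator; it does not count a failure. SAP Section 6.2.5.1 applies the same imputation rule within the per-protocol analysis, and SAP Section 6 makes that analysis secondary to ITT.

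**Step 5: size.** The documents give no sample size or power for the binary endpoints, so there is no plan figure to reproduce; the stated sizing concerns Treg counts. The input is the allocation of 8 PT101 and 2 placebo per cohort (Protocol Section 9.1). One reclassified subject moves a rate by 1/n:

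| Group | n | Shift (percentage points) |
|---|---|---|
| PT101, one cohort | 8 | 1/8 = 12.5 |
| Placebo, one cohort | 2 | 1/2 = 50 |
| PT101, Cohorts 1-3 pooled | 3 × 8 = 24 | 1/24 = 4.2 |
| Placebo, Cohorts 1-3 pooled | 3 × 2 = 6 | 1/6 = 16.7 |

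Pooling across cohorts is an assumption. With all six cohorts, pooled placebo would be 12 and the shift 1/12 = 8.3.

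In terms of exact 95% intervals, 3/8 is 37.5% (8.5 to 75.5) and 2/8 is 25.0% (3.2 to 65.1). For pooled placebo, 1/6 is 16.7% (0.4 to 64.1) and 0/6 is 0% (0 to 45.9).

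**Step 6: frequency.** The documents give no rate of Table 1 starts. For an assumed rate q, the chance of at least one among n subjects is 1 − (1 − q)^n:

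| Assumed q | 30 subjects (Cohorts 1-3) | 6 placebo subjects |
|---|---|---|
| 2% | 1 − 0.98^30 = 45.5% | 1 − 0.98^6 = 11.4% |
| 5% | 1 − 0.95^30 = 78.5% | 1 − 0.95^6 = 26.5% |
| 10% | 1 − 0.90^30 = 95.8% | 1 − 0.90^6 = 46.9% |

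This is the chance of a starter. A misattributed response also needs the subject to stay, be assessed and meet the criteria, so its chance is lower.

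**The case against.** Five things can be said for the plan.

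- **PP2 fits this case.** Its criterion is close to the title of Protocol Table 1, and efficacy and concomitant medications are both listed by subject, so in arms of 8 and 2 a contaminated responder would be visible. This stands as partial mitigation. It does not correct the ITT rate.
- **The pathway is permitted, not required.** Protocol Section 4.5.2 allows removal from the study for lack of compliance or other reasons, and Section 3.1.5 sends subjects with a dose-limiting toxicity from stopping drug straight to the early termination visit. Part of Section 6.3.3 and the schedule of events are blacked out. This stands: a reader might infer that Table 1 starters will stay in and be counted as responders, but the documents show only that they can be.
- **Scoring observed data regardless of other therapy is a legitimate treatment-policy strategy.** It is, but neither document says that this is the strategy chosen.
- **Table 1 is broad.** It includes antidiarrheals with a stated exception, and Section 5.2.2 gives safety as well as efficacy as grounds for the prohibitions. Any rule must respect the exception, and one cannot say that the drugs are barred for efficacy reasons alone.
- **The stakes are modest.** The endpoints are exploratory, the analyses are called descriptive, and the intervals are wide whichever way one subject is scored. This stands and limits the weight of the point.

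**Conclusion.** The gap is real. As written, the plan permits a subject who starts a Table 1 medication to be scored as an ITT responder at Week 12, in either arm, and PP2 closes this only in part. One such subject is worth 12.5 points on PT101 or 50 on placebo within a cohort, and 4.2 or 16.7 if Cohorts 1-3 are pooled. This rests on the planned 8:2 allocation, and on the subject staying in the study and meeting the response criteria. The frequency is unknown.

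Two stronger readings are tempting and are not supported. A reader might infer that the trial's main conclusions are at risk; the primary safety endpoint and the Treg-based sample size are untouched. A reader might also infer that stopping study drug for UC worsening should itself count as non-response; that does not follow, because no other drug need be involved. The point merits a correction to the SAP but does not call the design into question.

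**What to change.** Add to SAP Section 6.2.4.1: for the Table 5 endpoints, a subject who starts a Protocol Table 1 prohibited medication for UC before the assessment timepoint is a non-responder from that time, except limited antidiarrheal use approved under the Table 1 footnote. Keep the as-observed (treatment-policy) analysis as a sensitivity analysis.

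The cost is one sentence and one extra set of binary tables. The downside is that the main estimand becomes composite rather than treatment-policy; the sensitivity analysis still shows the latter. The change belongs before database lock, since SAP Section 1.1 requires later changes to be explained in the study report. It would not alter outputs for the DRC safety assessment, which SAP Section 4.3 presents as observed.

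The two statements in Protocol Section 5.2.2, that study drug must be stopped and that stopping may be required, should be reconciled by the sponsor. SAP Section 6.2.2.1 is equally silent on Table 1 starters for the continuous endpoints and could state its approach at the same time.

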#### 6.2.5 SENSITIVITY ANALYSES

##### 6.2.5.1 Per-Protocol Analysis

To evaluate the robustness of the efficacy analysis, the binary endpoint based on the NRI in the PP will use the same analysis methods for ITT as described in [Section 6.2.1](#).

## 7 PHARMACOKINETIC AND PHARMACODYNAMIC ANALYSES

### 7.1 PHARMACOKINETIC ASSESSMENTS

Blood samples for PK assessment will be collected as outlined in the protocol and outlined in [Appendix A](#). The PK endpoints will include change in serum concentration of PT101 over time and analysis of PK parameters. PK parameters for PT101 will be estimated using noncompartmental analysis (NCA) methods. PK parameters that will be assessed are shown in [Table 7](#). The maximum concentration ( $C_{max}$ ) for each subject will be determined along with the actual time it occurs ( $T_{max}$ ). As there are multiple doses given prior to complete elimination, the terminal elimination constant ( $K_{el}$ ) will be estimated from the concentrations observed following the final concentration peak. If there exists at least one observed concentration following the final peak, log-linear regression will be used to estimate the slope of the

concentration-time curve, the absolute value of which will be the  $K_{el}$ . From this, the terminal elimination half-life ( $t_{1/2}$ ) will be estimated using the formula:

$$t_{1/2} = \ln 2 / K_{el}.$$

The area under the concentration-time curve (AUC) from zero to infinity will be estimated in two parts: (1) AUC from zero to last observed concentration; and (2) AUC from last observed to infinity.

$$AUC_{0-\infty} = AUC_{0-t_{last}} + AUC_{t_{last}-\infty}.$$

The portion of the AUC up to the last observed concentration will be estimated using the log-linear trapezoidal method. The incremental portions of the AUC between each observed concentration will be estimated individually and summed to give the AUC across the period. The absorption phase will use a linear interpolation.

$$AUC_i = \frac{1}{2}(C_1 + C_2)(t_2 - t_1).$$

While the elimination phase will use a logarithmic interpolation, following the equation below.

$$AUC_i = \frac{C_1 - C_2}{\ln C_1 - \ln C_2} (t_2 - t_1).$$

The portion of the AUC following the last observed concentration will be assumed to follow an exponential elimination dictated by the terminal elimination constant. It will be estimated as follows:

$$AUC_{t_{last}-\infty} = \int_{t_{last}}^{\infty} C_{last} \cdot e^{-K_{el} \cdot t} dt = \frac{C_{last}}{K_{el}}.$$

**Table 7. Standard Pharmacokinetics Parameters**

Name	Description
$C_{max}$	Maximum concentration in a dosing interval
$C_{min}$	Minimum concentration in a dosing interval
$T_{max}$	Time of occurrence of $C_{max}$ within a dosing interval
$t_{1/2}$	Terminal elimination half-life
$AUC_{0-t}$	Area under the concentration-time curve from time 0 to the last measurable concentration in a dosing interval
$AUC_{0-\infty}$	Area under the concentration-time curve from time 0 extrapolated to infinity
$CL/F$	Apparent total body clearance following administration
$V_d/F$	Apparent volume of distribution following administration

Serum concentrations of PT101 will be listed and summarized by treatment group using descriptive statistics. PK parameters will be calculated using the actual time of sample collection whereas nominal time will be used for graphical presentations. Summary statistics including arithmetic mean, geometric mean, % coefficient of variation, SD, median, minimum, and maximum of the PK parameters listed in [Table 7](#) will

be summarized. All individual PK parameters will be listed in a by-subject listing. PK parameters will be analyzed for the PK & Biomarker analysis set.

Graphical presentations will use the nominal time of sample collection. Mean and median concentration time profiles will be calculated by dose-level (cohort) and nominal time and plotted on linear and semi-log transformed scales. The mean profiles will include SD error bars to indicate precision in the observed mean concentration; median profiles will include the minimum and maximum observed values. Individual and mean PT101 concentration time profiles will also be produced on linear and semi-log transformed scales for each cohort at CCI. Mean and median trough concentration time profiles will be calculated by cohort and nominal time and plotted on linear and semi-log transformed scales. Individual and mean trough concentration time profiles will be plotted on linear and semi-log transformed scales for each cohort.

Dose-proportionality of CCI will be assessed using a linear regression fit of  $\ln(AUC/C_{max})$  versus  $\ln(\text{Dose})$  to estimate slope and confidence interval of slope. Natural log-transformed exposures versus natural log-transformed dose relationship for both  $AUC_{0-\infty}$  and  $C_{max}$  will also be presented.

## 7.2 IMMUNOGENICITY ASSESSMENTS

For all dosing cohorts (refer to [Appendix A](#) for dosing schedule), blood samples for immunogenicity / anti-drug antibody (ADA) analyses will be collected. ADA to PT101 will be assessed using a standard 3-tier approach to measure binding antibody with a screening assay, ADA titer using a confirmatory assay, and neutralizing antibody to PT101 in subjects with confirmed positive titers. Summary statistics including number and percentage of subject ADA status and titer by dose for each cohort will be presented. A by-subject listing of ADA status and titers by dose will also be provided.

To assess the impact of ADA on the concentration of PT101, individual PK profiles from ADA positive and ADA negative subjects will be plotted on both a linear scale and log scale at their relevant dose levels and for each dosing regimen CCI evaluated. Impact of ADA on the PD markers that will be the most affected by PT101 may also be graphically investigated via e.g., box plots of PT101 PK parameters by ADA status or ADA titer versus time profiles. Immunogenicity assessments will be analyzed for the PK & Biomarker analysis set.

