All analyses will be descriptive in nature, with point and 95% interval estimates, if necessary, provided for the following parameters of interest, separately for each available PT101 dose level/dosing regimen and placebo unless otherwise specified in the SAP:

- Mean change in total Mayo Scores, modified Mayo Score, RHI score, UC-100 score, and PROs (IBDQ, SF-36) at Week 12
- Mean change from baseline in partial Mayo Score, FC, and hs-CRP levels at assessed timepoints through Week 12
- Mean change from baseline in partial Mayo Score beyond Week 12

- Proportion of subjects achieving clinical remission, endoscopic improvement, clinical response, endoscopic remission, histologic remission, histologic response, mucosal healing at Week 12
- Proportion of subjects achieving symptomatic remission and symptomatic response at assessed timepoints through Week 12

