### 4.2.1 INTENT-TO-TREAT ANALYSIS SET

The intent-to-treat analysis set (ITT) consists of all randomized subjects. Subjects will be included in the treatment group assigned at randomization regardless of the actual treatment received. All efficacy endpoints will be analyzed based on the ITT.

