### 4.2.5 PK & BIOMARKER ANALYSIS SET

The PK & biomarker analysis set will include all randomized subjects who receive at least 1 dose of study drug and who have at least one valid analytical result at baseline, at least one post-dose analytical result and had no major relevant protocol or dosing deviations that could potentially affect the PK and/or PD profile. The PK & biomarker analysis set will be used for the summaries of all PK, PD, and biomarker data. All PK, PD, and biomarker parameters are summarized in [Section 7](#).

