## 8 BIOMARKER ANALYSES

Relationships of biomarker parameters (e.g., baseline values, changes from baseline) to efficacy, safety, and PK parameters will be explored. Relationships and associated data that are determined to be of interest will be summarized. Biomarker analysis will be analyzed for the PK & Biomarker analysis set.

Listings and descriptive statistics (n, mean, median, SD, CV%, minimum, and maximum) will be provided by treatment group for each biomarker specified in **Table 9** as follows:

- Baseline values
- Values at each post-baseline visit
- Absolute change from baseline at each post-baseline visit
- Fold Change from baseline at each post-baseline visit

In addition, the following figures will be generated for sCD25, IL-5, IFN- $\gamma$ , IL1-B, IL-2, IL-4, IL-6, IL-8, IL-10, IL12p70, IL-13, TNF-a, and FOXP3, and CD4:

- Mean plot of absolute level aggregated and separated by treatments
- Mean plot of fold change from baseline aggregated and separated by treatments
- Mean plot of absolute change from baseline aggregated and separated by treatments

All other biomarker analysis will be included in a separate Translational SAP.

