**Table 9. Definition of Biomarker Endpoints**

Measure	Definitions	Analysis Timepoint
FC	Mean change from baseline in fecal calprotectin	CCI
hs-CRP	Mean change from baseline in high sensitivity C-reactive protein levels	
sCD25	Mean change from baseline in sCD25	
IL-5	Mean change from baseline in IL-5	
IFN- $\gamma$	Mean change from baseline in IFN- $\gamma$	
IL-1	Mean change from baseline in IL-1	
IL-2	Mean change from baseline in IL-2	
IL-4	Mean change from baseline in IL-4	
IL-6	Mean change from baseline in IL-6	
IL-8	Mean change from baseline in IL-8	
IL-10	Mean change from baseline in IL-10	
IL12p70	Mean change from baseline in IL12p70	
IL-13	Mean change from baseline in IL-13	
TNF-a	Mean change from baseline in TNF-a	
FOXP3	Mean change from baseline in TSDR FOXP3 Assay (Treg cells) (% and cells/ $\mu$ l)	
CD4	Mean change from baseline in TSDR CD4 Assay (CD4 T cells) (% and cells/ $\mu$ l)	

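### ADA, fecal calprotectin and hs-CRP are summarised only in a set that drops whole subjects for major deviations relevant to PK/PD; ADA in all evaluable treated subjects, and the two markers in the ITT, would cost almost nothing

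*SAP*

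**What the plan says.** SAP 4.2.5 defines one PK & Biomarker set for dosed, randomised subjects "who have at least one valid analytical result at baseline, at least one post-dose analytical result" and who "had no major relevant protocol or dosing deviations that could potentially affect the PK and/or PD profile". All these conditions apply to the subject, not to a sample or dosing interval. The scope sentence in 4.2.5 names PK, PD and biomarker data. It does not name immunogenicity.

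Two later sections assign further endpoints to the set:

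- **SAP 7.2, ADA:** "Immunogenicity assessments will be analyzed for the PK & Biomarker analysis set". ADA is a secondary endpoint (Protocol 2.2.2).
- **SAP 8:** "Biomarker analysis will be analyzed for the PK & Biomarker analysis set". Table 9 there includes "Mean change from baseline in fecal calprotectin" and "Mean change from baseline in high sensitivity C-reactive protein levels".

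For efficacy, SAP 4.2.1 says: "All efficacy endpoints will be analyzed based on the ITT". Table 6 of the SAP lists the partial Mayo Score among the continuous efficacy endpoints and omits FC and hs-CRP. Protocol 9.3.4, headed Safety and Efficacy Analyses, groups all three in one line: "Mean change from baseline in partial Mayo Score, FC, and hs-CRP levels at assessed timepoints through Week 12".

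**The concern.** The deviation condition was written for PK and PD profiles. A dosing error can make a half-life or an AUC uninterpretable, and leaving out that subject's PK is defensible. ADA incidence asks a different question: among people who received PT101 and gave an evaluable sample, how many formed antibodies? A treated subject with a dosing error still answers it.

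For FC and hs-CRP the issue is consistency. They help interpret the clinical scores, yet they would be summarised by group on a population selected partly by events after randomisation, while the partial Mayo Score is summarised on everyone randomised. A difference between the marker result and the clinical result could then come from different subjects.

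At stake is the loss of valid data from a small study. SAP 4.2 applies the same sets to the periodic reviews, and SAP 13 allows immunogenicity and biomarker summaries in DRC packages, so the selection could also be present when dose and regimen are discussed.

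**Working it through.** This is mainly a comparison of text. The arithmetic only shows scale. The plan gives no ADA, FC or hs-CRP figure to reproduce; its one design figure, 80% power, concerns the Treg count.

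**1. Which set applies**

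| Endpoint | Place in Protocol | SAP analysis set | Other version stated in SAP |
|---|---|---|---|
| Partial Mayo Score | 9.3.4 | ITT (4.2.1, Table 6) | FAS if different; PP |
| FC | 9.3.4 and 7.5.2 (biomarker) | PK & Biomarker (8, Table 9) | none |
| hs-CRP | 9.3.4 and 7.5.2 (biomarker) | PK & Biomarker (8, Table 9) | none; CRP is in the safety chemistry panel |
| ADA | 2.2.2 (secondary) | PK & Biomarker (7.2) | none |

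**2. Whether an excluded subject can be recovered elsewhere**

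- *Listings.* SAP 7.2 promises a by-subject ADA listing, but SAP 4.1 limits listings to subjects in the relevant analysis set. An excluded subject's ADA result could be absent from both table and listing.
- *Sensitivity analysis.* SAP 6.2.5 covers binary efficacy endpoints only.
- *Blinded decision.* SAP 4.2.3 requires a blinded data review for the per-protocol exclusions. Nothing equivalent is stated for the PK & Biomarker set.
- *CRP.* Protocol 7.6.2 includes CRP in the chemistry panel, and SAP 9 and 9.4 summarise laboratory tests in the Safety Set with change from baseline. This partly covers hs-CRP, though not necessarily the high-sensitivity assay. It does not cover FC or ADA.

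**3. Scale**

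Inputs: 8 PT101 and 2 placebo subjects per planned cohort of 10 (Protocol synopsis and 9.1). The ADA counts are assumptions.

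Weight of one exclusion: 1/8 = 12.5% of a cohort's active arm, or 1/2 = 50% of its placebo arm.

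ADA incidence = positives / subjects in the set, with exact (Clopper-Pearson) 95% intervals:

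| Case | Count | Incidence | 95% CI |
|---|---|---|---|
| No exclusion | 3/8 | 37.5% | 8.5 to 75.5% |
| One ADA-positive subject excluded | 2/7 | 28.6% | 3.7 to 71.0% |
| One ADA-negative subject excluded | 3/7 | 42.9% | 9.9 to 81.6% |
| No exclusion | 1/8 | 12.5% | 0.3 to 52.7% |
| The one positive subject excluded | 0/7 | 0% | 0 to 41.0% |
| One ADA-negative subject excluded | 1/7 | 14.3% | 0.4 to 57.9% |

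One exclusion moves the estimate down by 8.9 points (37.5 − 28.6) or up by 5.4 (42.9 − 37.5) in the first example. In the second it moves down by 12.5 points or up by 1.8 (14.3 − 12.5). The intervals overlap almost completely. The practical loss is of a valid observation, most visibly when it is a cohort's only positive result.

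**The case against.** The case for leaving the text alone has real force.

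- **Few subjects may be affected.** Only deviations that are both major and relevant to PK/PD exclude. Interruptions and stops that the protocol itself requires (Protocol 3.1.5 to 3.1.7) are not deviations. A reader might infer that anyone with irregular dosing is lost; the wording does not support that. This stands, and it limits the likely size.
- **FC and hs-CRP are biomarkers in the SAP.** A reader might infer that the SAP moved two efficacy endpoints out of the ITT and should have recorded this in Section 14. The documents do not support that. The protocol never assigns them to the ITT, describes them under biomarker assessments as well as in 9.3.4, and allows the SAP to add sets (9.3.2.4). What stands is a mismatch with the partial Mayo Score, not a breach of the SAP's ITT rule.
- **The planned summaries are descriptive.** SAP 8 plans listings, summary statistics and plots for these markers. With 2 placebo subjects per cohort there is little within-cohort comparison to lose. This stands, so it would be too strong to say that a randomised comparison is forfeited.
- **The baseline condition.** A reader might infer that valid post-dose PK data are discarded when the pre-dose PT101 sample is missing. SAP 4.2.5 does not say the baseline result must be a PT101 concentration, so this is not shown. For FC and hs-CRP, a subject without baseline contributes no change in any population.
- **A shared set has a use.** SAP 7.2 plots PK by ADA status, which needs both measures on the same subjects. This justifies the set for those plots, not for ADA incidence.
- **The proposed ADA set also depends on a post-dose sample.** True. The gain is removal of the deviation condition, not of all selection.

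**Conclusion.** The point holds as a free improvement. As written, the SAP could drop valid ADA and FC results, and hs-CRP results from their main summary, for reasons that concern the PK/PD profile. It states no alternative population for ADA or FC, and no blinded review of exclusions from this set.

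The weight of each exclusion is known: 12.5% of a cohort's active arm at the planned 8 subjects. The number of exclusions, and whether they relate to ADA status or inflammation, is not. A reader might infer that ADA incidence will be understated. Nothing in the documents links deviations to ADA status, and the assumed counts move in either direction, within wide sampling error. If no subject has such a deviation, the deviation condition has no effect.

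**What to change.** In the SAP:

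1. **ADA (7.2).** Summarise and list ADA incidence and titer for all Safety Set subjects given PT101 with at least one evaluable post-dose ADA sample.
2. **FC and hs-CRP (8, Table 9).** Summarise change from baseline in the ITT, as observed, by randomised group, to match the partial Mayo Score population.
3. **PK & Biomarker set (4.2.5).** Keep it for PK and PD and for the PK-by-ADA plots.

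The cost is a few sentences and extra population flags in the analysis datasets. No new data are needed, and no sample-size or design figure changes.
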